5.5 Concurrent Medications

5.5.1 Prohibited Medications

Subjects who require any prohibited medications during the 52-week study will have study agent discontinued, they will, however, remain on study and continue to be assessed according to the schedule outlined in the Study Calendar ([Table 6-1](#)). The following medications are prohibited during the study:

- Other investigational agents (biologic or non-biologic). Investigational applies to any drug not approved for sale in the country it is being used.
- Anti-TNF therapy (eg, adalimumab, etanercept, infliximab)
- Other biologicals (eg, commercial belimumab, rituximab, abatacept, interleukin-1 receptor antagonist [anakinra])
- Live vaccines

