8.5.4 Analysis of Major Efficacy Endpoint

The percent of subjects with average prednisone (or equivalent) dose that has been reduced by $\geq 25\%$ from baseline to ≤ 7.5 mg/day during Weeks 40 through 52 will be compared between the belimumab and the placebo groups using a logistic regression model, adjusted for baseline prednisone (or equivalent) dose level, baseline SELENA SLEDAI score (≤ 9 vs ≥ 10), and region (US/Canada or Central America/South America/Mexico or Europe/Australia/Israel or Asia). The analysis will be performed on subjects who were using prednisone (or equivalent) at a dose > 7.5 mg/day at baseline. In the analysis, all subjects who drop out and/or add new immunomodulatory agents before the Week 52 visit will be considered having no steroid reduction. However, switching immunomodulatory agents for toxicity reasons or lack of availability (eg, no longer manufactured or no longer reimbursed) is permitted and will not be imputed as no steroid reduction. To examine the robustness of the results, a sensitivity analysis of the steroid reduction may be performed without considering any information related to the use of new immunomodulatory agents.

Analysis of other efficacy endpoints will be described in the analytical plan.

9 Pharmacogenetics (PGx)

This is an optional sub-study. The IEC/IRB and, where required, the applicable regulatory agency must approve the PGx assessments before these can be conducted at the study site. The approval(s) must be in writing and clearly specify approval of the PGx assessments (ie, approval of [Appendix 7](#)). In some cases, approval of the PGx assessments can occur after approval is obtained for the rest of the study. If so, then the written approval will clearly indicate that approval of the PGx assessments is being deferred and the study, except for PGx assessments, can be initiated. When PGx assessments are not approved, then approval for the rest of the study will clearly indicate this and that PGx assessments will not be conducted.

In consenting subjects, a blood sample for PGx research will be drawn to better characterize genetic variability (eg, HLA typing) that may affect efficacy or safety endpoints. Information regarding PGx research is included in [Appendix 7](#).

10 Study Administration

This study is sponsored by GlaxoSmithKline (GSK) LLC. GSK will lead the operational conduct of this study on a world-wide basis working with contract research organizations.

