- For the major efficacy endpoint (steroid dose reduction), the protocol states that if a subject switches immunomodulatory medications for reasons other than toxicity or lack of availability they should be considered a non-responder. However, the eCRF has not been designed to collect data on reasons for switches and therefore all new immunomodulatory agents to treat SLE will render a subject a non-responder in the analysis. Hence, subjects who switch will be considered non-responders regardless of the reason for switching. Additionally prednisone analyses and summaries are based only on steroids used to treat SLE (see Section [9.5.16](#) and Section [12.1.1](#)).
- “Immunomodulatory medications” will be identified as immunosuppressants (ATC code beginning “L04A”) plus cyclophosphamide and mercaptopurine, per the definition used across the Benlysta program.
- The number of hospitalizations per patient and percent of patients hospitalized will be derived from the SAE data. See Section [9.3](#) for further detail.
- SLICC/ACR Damage Index is not explicitly stated as an endpoint in the protocol. However, this is an endpoint of interest and therefore analyses will be performed as described in Section [12.2.3](#).

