9.5.16. Prednisone

All prednisone analyses and summaries will consider SLE-related steroids only but data will also be derived for all indications steroids (SLE and non-SLE) for reference where indicated below.

The following will apply to all derivations in this section unless otherwise stated:

- For steroid use analyses, all steroid dosages are converted to a prednisone equivalent in milligrams; therefore, analyses refer to average daily prednisone dose instead of average daily steroid dose. See [Appendix 4: Prednisone Equivalent Conversion](#) for instructions on converting steroids to prednisone equivalents.
- This appendix will be updated throughout the course of the study to include all corticosteroids taken by subjects and will be finalized prior to the first database release and unblinding.
- For all derivations of the average daily prednisone equivalent dose including baseline, days on which a subject does not have prednisone use recorded will be considered as 0 mg for the day.
- Steroids taken intravenously (IV), intramuscularly (IM), subcutaneously (SC), intradermally, and orally are considered in prednisone dose derivations only.
- All steroids taken on any given day, including overlaps, will be accounted for in calculations of average daily prednisone dose. To achieve this programmatically, each entry is converted to the prednisone equivalent daily dose (see [Appendix 4: Prednisone Equivalent Conversion](#)) and the sum of the prednisone equivalent doses on Day X gives the total prednisone equivalent daily dose on Day X. For example, if two steroids are given on the same day they will be converted to a prednisone equivalent daily dose and then added together to achieve a total for that day.

Steroids used to treat SLE are those with medication type corticosteroid for SLE (SDTM.CM.CMCAT = 'CORTICOSTEROID FOR SYSTEMIC LUPUS ERYTHEMATOSUS').

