9.5.17. Immunomodulatory Medications

Immunomodulatory medications are identified as all immunosuppressants with ATC code beginning “L04A” plus cyclophosphamide and mercaptopurine. For further detail see [Appendix 3](#): SLE Allowable Medication Categories.

Only immunomodulatory medication used to treat SLE will be included in summary tables of immunomodulatory medication usage (with the exception of the concomitant medication summaries which will include all medications). These are identified as those with a medication type of treatment for SLE (SDTM.CM.CMCAT = ‘SYSTEMIC LUPUS ERYTHEMATOSUS’).

It will be determined whether immunomodulatory agents are being received at any given reference date by using medication start and stop dates as follows:

- Start date and stop date are prior to reference date → subject is not on immunomodulatory agents
- Start date on or before date and stop date on or after reference date → subject is on immunomodulatory agents
- Start date on or before reference date, stop date is missing and medication is ongoing → subject is on immunomodulatory agents

Status of immunomodulatory medication is assessed at the following dates (i.e. these are the reference dates for the above derivation):

- Baseline
- Treatment completion date in treatment completers (Section [9.5.7](#))

It is also assessed for shift tables from baseline to:

- Treatment completion date (treatment completers)
- Study agent discontinuation date (subjects who prematurely discontinued study agent)

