12.1. Major Efficacy Analyses

12.1.1. Percent of Subjects with Prednisone Reduction by $\geq 25\%$ from baseline to ≤ 7.5 mg/day during Week 40 through Week 52

Primary Analysis

For this analysis, only steroids used to treat SLE will be included and only subjects with a baseline average daily prednisone dose >7.5 mg/day will be included. See Section 9.5.16.1 for derivation of baseline prednisone dose and Section 9.5.16.2 for derivation of average prednisone use between Week 40 to Week 52.

The percent of subjects whose average prednisone dose has been reduced by $\geq 25\%$ from baseline to ≤ 7.5 mg/day during Weeks 40 through 52 will be compared between belimumab and placebo using a logistic regression model. Independent variables in the model will include treatment group, baseline prednisone dose, and the following

randomization stratification factors per the eCRF: screening SELENA SLEDAI score (≤ 9 vs. ≥ 10), and region. A responder is defined as having a prednisone reduction by $\geq 25\%$ from baseline to ≤ 7.5 mg/day during Weeks 40 through 52.

Any subject who withdraws from the study or adds new immunomodulatory agents used to treat SLE (note that this will include switches) prior to the Week 52 visit will be considered having no steroid reduction.

A summary of the number and percentage of subjects who are responders by treatment group, the treatment difference versus placebo, the odds ratio and 95% CI versus placebo, and a p-value for the odds ratio will also be provided.

Sensitivity Analysis

- To examine the robustness of the results, a sensitivity analysis of the SLE-related steroid reduction will be performed without considering any information related to the use of new immunomodulatory agents (note that this will include switches).

Additional Summaries of Prednisone

- A summary of the number and percentage of subjects with average SLE-related daily prednisone dose ≤ 7.5 mg/day and > 7.5 mg/day at baseline (Day 1) and treatment completion date will be presented for treatment completers.
- The cumulative SLE-related prednisone dose will be derived as described in Section 9.5.16.3. A table of descriptive statistics will be presented including the mean, standard deviation, median, 25th and 75th percentiles, minimum and maximum.
- A listing of cumulative SLE-related prednisone dose will be displayed by treatment and subject.

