15.4. Appendix 4: Prednisone Equivalent Conversion

- A concomitant medication is identified as a steroid if at least one associated ATC code (ATCCD1 – ATCCD6) begins with ‘H02.’
- The following routes are considered to provide systemic exposure: oral, subcutaneous, intramuscular, intradermal, and intravenous. Topical routes of administration are excluded (e.g., topical, conjunctival, intranasal).
- At data base release, all preferred terms identified with an ATC code beginning with ‘H02’ will be reviewed to ensure a conversion factor exists for all terms with a systemic route of administration.
- Similarly, all routes of administration for preferred terms with an ATC code beginning with ‘H02’ will be reviewed to ensure all systemic routes have been identified in the list above.
- In order to be converted the frequency and dose of the steroid must be present with the unit dose in milligrams (mg).
- Reported dose for systemic steroid is converted to prednisone equivalent dose using conversion factor for each particular medication (refer to online calculator <http://www.globalrph.com/corticocalc.htm>).

A two-step process will be used to calculate the prednisone equivalent daily dose:

1. $DOSE2$ (prednisone equivalent dose in mg) = $DOSE$ (collected dose in mg) x Conversion Factor
2. DD (daily dose in mg/day) = $DOSE2$ (prednisone equivalent dose in mg) x Frequency Factor

Where multiple steroids are taken on one day, the sum of these will be the prednisone equivalent daily dose. An intermediate dataset will contain the total daily prednisone equivalent daily dose for each study day. This will be used to derive prednisone endpoints.

Preferred term	Conversion factor for converting to a prednisone-equivalent dose
BETAMETHASONE	8.333
BETAMETHASONE DIPROPIONATE	8.333
BETAMETHASONE SODIUM PHOSPHATE	8.333
BETAMETHASONE VAL	8.333
BETROSPAM	8.333
CELESTONA BIFAS	8.333
CORTISONE	0.2
CORTISONE ACETATE	0.2
CRONOLEVEL	8.333
DEFLAZACORT	0.8333
DEPO-MEDROL MED LIDOKAIN	1.25
DEXAMETHASONE	6.667

Preferred term	Conversion factor for converting to a prednisone-equivalent dose
DEXAMETHASONE ACETATE	6.667
DEXAMETHASONE PHOSPHATE	6.667
DEXAMETHASONE SODIUM PHOSPHATE	6.667
FLUCORTOLONE	3
HYDROCORTISONE	0.25
HYDROCORTISONE ACETATE	0.25
HYDROCORTISONE HYDROGEN SUCCINATE	0.25
HYDROCORTISONE SODIUM SUCCINATE	0.25
MEPREDNISONE	1.25
METHYLPREDNISOLONE	1.25
METHYLPREDNISOLONE ACEP	1.25
METHYLPREDNISOLONE ACETATE	1.25
METHYLPREDNISOLONE HEMISUCCINATE	1.25

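### The steroid-responder rule makes no use of the SAP's own Prohibited-medication category, and the scoring of PRN and unknown-frequency steroid days is left open

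*SAP*

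**What the plan says.** References to the SAP are to the Week 52 reporting and analysis plan unless stated otherwise.

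**Failing events.** SAP Section 12.1.1 gives two: "Any subject who withdraws from the study or adds new immunomodulatory agents used to treat SLE". Section 2.2.3 repeats the second and includes switches: "all new immunomodulatory agents to treat SLE will render a subject a non-responder in the analysis". Protocol Section 8.5.4 has the same pair: "all subjects who drop out and/or add new immunomodulatory agents before the Week 52 visit will be considered having no steroid reduction". Stopping study agent is not on the list.

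**Which drugs count.** Section 9.5.17: "Immunomodulatory medications are identified as all immunosuppressants with ATC code beginning" L04A, plus cyclophosphamide and mercaptopurine. For the usage summaries only SLE records are kept: "These are identified as those with a medication type of treatment for SLE". The responder rule has its own restriction to SLE use.

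**Prohibited drugs.** Protocol Section 5.5.1: "Subjects who require any prohibited medications during the 52-week study will have study agent discontinued, they will, however, remain on study". SAP Appendix 3 (Section 15.3) has a separate Prohibited category defined by drug name. It holds several biologics, belimumab, immunoglobulin and a generic investigational-drug term. Section 12.1.1 does not refer to it.

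**Steroid dose.** Under Section 9.5.16, "days on which a subject does not have prednisone use recorded will be considered as 0 mg for the day". Appendix 4 (Section 15.4) converts a record only if dose, frequency and a milligram unit are available. Its frequency table gives PRN and UNK a Null factor.

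**The concern.** The rule treats escalation of SLE therapy as failure, so that a lower steroid dose achieved with another drug is not credited to study treatment. Prohibited drugs are the clearest form of escalation, yet they are caught only indirectly, through an ATC code and an indication field. Commercial belimumab is the most pointed case. SAP Section 10.4 foresees subjects stopping study agent, starting it and continuing monthly visits, but plans only a listing. A placebo subject who moves to the active drug in this way should not be able to count as a placebo responder.

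On steroids, a subject still taking the drug under a PRN or unknown-frequency record might be scored as taking none. Two competent programmers could classify the same subject differently on an endpoint tested at the two-sided 0.05 level.

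**Working it through.** The documents give no responder rate, subgroup size or power for this endpoint, so there is no figure of the plan's to reproduce. The check sets the rules side by side and then runs the dose derivation on examples.

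**1. Prohibited drug against each failing event**

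- *Study withdrawal:* not met. Protocol Sections 3.1 and 5.5.1 and SAP Section 10.4 keep these subjects on study.
- *New SLE immunomodulator:* met only if the drug has an L04A code (or is cyclophosphamide or mercaptopurine) **and** is used to treat SLE. No ATC code is given for any drug in the Prohibited list.
- *Sensitivity analysis in Section 12.1.1:* ignores all new immunomodulators. Any biologic user who stays on study and meets the dose target is a responder there, so it widens the gap and does not test it.

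**2. Null frequency in Weeks 40 to 52**

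Inputs: Section 9.5.16.2 formula; example subject with baseline 10 mg/day, Week 40 visit on Day 281 and completion on Day 365. The sum runs over Days 282 to 364 (83 days) and the divisor is 365 − 281 = 84. Response needs an average ≤ 7.5 mg and ≤ 0.75 × 10 = 7.5 mg.

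| Record | Null summed as 0 | Null treated as missing |
|---|---|---|
| 10 mg once daily | 83 × 10 / 84 = 9.88 mg, non-responder | the same (no Null) |
| 10 mg, UNK frequency | 0 mg, responder | average missing |
| 5 mg once daily + 20 mg PRN | 83 × 5 / 84 = 4.94 mg, responder | average missing |

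For a study completer with a missing average, no rule assigns an outcome. Section 9.5.16.2 foresees a missing average only after withdrawal before Week 40, and Section 9.4.3 bars imputation unless stated.

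**3. Null frequency at baseline**

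The same conversion feeds the 7-day baseline average (Section 9.5.16.1). A subject whose only baseline record is 10 mg UNK has a baseline of 0 or missing, and so leaves the > 7.5 mg/day subgroup. A subject on 8 mg once daily plus PRN use has a baseline of 8 mg if Null is 0, and must then reach 0.75 × 8 = 6 mg, a harder target than 7.5 mg. The baseline effect can therefore work against response.

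**4. Scale, on assumptions only**

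Assume true responder rates of 10% (placebo) and 15% (belimumab), or 12% and 17%. Let a fraction f of non-responders be counted as responders, so p′ = p + f(1 − p).

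- *Placebo only, f = 1%:* 0.10 + 0.01 × 0.90 = 0.109. The odds ratio falls from (0.15/0.85)/(0.10/0.90) = 1.59 to (0.15/0.85)/(0.109/0.891) = 1.44. For 12% and 17% it falls from 1.50 to 1.39.
- *Placebo only, f = 3%:* placebo becomes 0.127 or 0.1464, and the odds ratio 1.21 or 1.19.
- *Both arms, f = 1%, 10% and 15%:* belimumab becomes 0.15 + 0.01 × 0.85 = 0.1585. The odds ratio is (0.1585/0.8415)/(0.109/0.891) = 1.54.

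The effect thus depends mainly on imbalance between arms. Nothing in the documents informs f or that imbalance.

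**The case against.** The strongest objection is that the L04A clause may already do most of the work. It does not exclude biologics. A drug qualifies if any one of up to six ATC codes begins L04A, and nothing makes the Appendix 3 categories mutually exclusive. A reader might infer that every subject given a prohibited biologic escapes the rule. The documents do not support that: a biologic coded L04A and recorded for SLE makes the subject a non-responder. What remains is narrower. The rule depends on codes the SAP does not show, while an existing name-based list goes unused. Nothing shows that the investigational-drug or immunoglobulin terms carry L04A. The SAP itself adds cyclophosphamide and mercaptopurine by name, so it did not treat L04A as complete. Immunoglobulin needs a caveat: the protocol's prohibited list does not name it, so it cannot be said that those subjects stop study agent.

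A reader might also infer that PRN and unknown-frequency days are set to 0 mg and so favour response. The 0 mg sentence concerns days without recorded use, and a PRN day has recorded use. Zero is one possible programming outcome, and missing is another. Because baseline is affected too, the direction is not established.

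Existing safeguards reduce the likely number of cases. Protocol Section 5.5.2 requires corticosteroid dose and frequency to be recorded. Appendix 4 converts several non-milligram units, and additions to its factors are to be documented before unblinding. They do not settle the scoring, because PRN and UNK are already in the table as Null.

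Finally, efficacy is secondary in this safety study, and the SAP follows the protocol's two failing events. Both are true and limit the priority of the point. Neither closes the gap.

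**Conclusion.** The point holds in limited form. As written, the rule lets a subject who starts a Prohibited-category drug be a responder if the drug is not coded L04A or not recorded as SLE treatment. The documents do not show which listed agents these are or how many subjects are affected, so the size of the bias is unknown. A bias towards no difference is plausible if such drugs are started more often on placebo, but that is an assumption. The odds ratios above show scale only and are not estimates.

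The scoring of Null-frequency steroid days is unspecified at baseline and in Weeks 40 to 52. This is a gap in specification, with no demonstrated bias in either direction.

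**What to change.** 1. Add to the non-responder rule in Section 12.1.1: *or starts any medication in the Appendix 3 Prohibited category, including commercial belimumab, before the Week 52 visit*. Exclude records clearly given for a non-SLE indication, so that such use is not scored as treatment failure. Report the number of added failures by arm.
2. State how PRN and UNK steroid days were handled, at baseline and in Weeks 40 to 52, and report the number of affected subjects by arm.
3. Add a sensitivity analysis scoring subjects with an unconvertible systemic SLE steroid record in Weeks 40 to 52 as non-responders. This should not replace the main analysis, since one PRN record is weak evidence of failure.

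The Years 2 to 5 plan (Section 1) records unblinding of the Week 52 data on 2 January 2019. Any re-analysis must therefore be labelled post hoc, with the original rule's result kept beside it.

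Cost: one clause, two sets of counts and one extra model run. The Prohibited category already exists. Unconvertible records would have to be identified from the dose, unit and frequency fields. The downside is that a few more subjects become non-responders.

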12.2. Other Efficacy Analyses

12.2.1. Immunomodulatory Agents to Treat SLE

The following summaries will present immunomodulatory agents used to treat SLE only, i.e. those with medication type 'SYSTEMIC LUPUS ERYTHEMATOSUS'.

- A summary of the number and percentage of subjects taking immunomodulatory agents to treat SLE by ATC level 4 term and preferred term will be displayed for the on-study period.
- A summary of the number and percentage of subjects on immunomodulatory agents to treat SLE at baseline (see Section 9.5.17 for derivation of baseline medication) and at the treatment completion date (in treatment completers as defined in Section 9.5.7 with a treatment completion date) will be presented.

A summary of the shift (on versus off immunomodulatory agents to treat SLE) from baseline category to treatment completion date (in subjects who completed IP as

scheduled) and at study agent discontinuation date (subjects who prematurely discontinued IP)

See Section 9.5.17 for detail on defining immunomodulatory medication use at baseline and treatment completion.

All immunomodulatory agents will be indicated in the listing of concomitant medications.

12.2.2. Hospitalizations

This information will be derived from the SAEs using the review process outlined in Section 9.3.

The number and percent of subjects hospitalized will be presented along with the number of hospitalizations per subject.

Subjects with hospitalizations and SAEs contributing to hospitalization will be indicated in the listing of SAEs and the number of hospitalization per subject (identified by clinical review, see Section 9.3) will also be listed.

12.2.3. SLICC/ACR Damage Index

SLICC/ACR is attached in [Appendix 5: SLICC/ACR Damage Index](#).

A listing of all available SLICC/ACR data will be provided, including the analysis result for each item, the total score and the change from baseline at Week 52.

12.2.3.1. SLICC/ACR Damage Index Change from Baseline at Week 52

The change from baseline in SLICC/ACR Damage Index score at Week 52 will be summarized for belimumab and placebo.

The table will display the summary statistics for the SLICC/ACR Damage Index score at baseline and at Week 52. The table will also display the mean change from baseline, standard deviation, median, 25th and 75th percentiles, minimum and maximum. Only subjects who complete the full course of study agent through 48 weeks and complete the study to Week 52 will be included in the summary at Week 52.

A separate summary will be produced for subjects who complete the study through 52 weeks, i.e. subjects with off-treatment data will be included. The table will display the summary statistics for the SLICC/ACR Damage Index score at baseline and at Week 52. The table will also display the mean change from baseline, standard deviation, median, 25th and 75th percentiles, minimum and maximum.

12.2.3.2. SLICC/ACR Damage Index Worsening at Week 52

The number and percentage of subjects with worsening in their SLICC/ACR Damage Index score compared with baseline at Week 52 will be presented. Worsening is defined as a change in score (Week 52 visit minus Baseline) >0. The percentage of subjects with

worsening in their SLICC/ACR Damage Index score at Week 52 will be compared between belimumab and placebo using a logistic regression model. The independent variables in the model will include treatment group and randomization strata per the eCRF: steroid dose (≤ 7.5 mg/day vs > 7.5 mg/day prednisone or equivalent used to treat SLE), region, screening SELENA SLEDAI score (≤ 9 vs. ≥ 10), and baseline SLICC/ACR Damage Index score.

The table will display the number and percentage of subjects with worsening in their SLICC/ACR Damage Index score by treatment group, the treatment difference versus placebo, the odds ratio and 95% CI versus placebo, and a p-value for the odds ratio.

Only subjects who complete the full course of study agent through 48 weeks and complete the study to Week 52 with a baseline and post-baseline assessment will be included in the analysis. See Section 9.5.19 for further detail.

A separate summary will present the number and percentage of subjects with worsening at Week 52 compared to baseline by organ domain in treatment completers who have a Week 52 SLICC assessment. Only subjects who have potential to worsen in a given domain will be summarized for that domain, i.e. subjects who do not have the maximum damage score for the domain at baseline.

A summary will also be produced for subjects who complete the study through 52 weeks, i.e. subjects with off-treatment data will be included. The table will display the number and percentage of subjects with worsening in their SLICC/ACR Damage Index score by treatment group and the treatment difference versus placebo.

Subgroups

The SLICC/ACR worsening at Week 52 will be summarized for treatment completers with a Week 52 assessment for subgroups listed in Section 8.3 using the eCRF data to derive randomization stratification factors.

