¹ A urine pregnancy test is required for women of child bearing potential. The results of urine pregnancy test must be available prior to dosing.

GlaxoSmithKline group of companies

- 2 The weight at the current visit should be used to calculate dose. Refer to Section 5.2 for further information.
- 3 Suicidality is to be assessed prior to study agent infusion using the "Since Last Visit" C-SSRS (Appendix 5).
- 4 Subjects should remain under clinical supervision for 3 hours after completion of the first 2 study agent infusions. Should symptoms of acute hypersensitivity occur, an extended period of monitoring may be appropriate, based on clinical judgment.
- 5 All SAEs will be recorded. These data will be used to analyze serious infections and selected serious psychiatric events.
- 6 Guidelines for opportunistic infections and other infections of interest are provided in Appendix 2.
- 7 A hospitalization is an inpatient admission for any length of time. An admission for administration of study agent, for routine or planned clinical procedures, or for "social" reasons (not the result of any adverse change in the subject's condition) should not be recorded as a hospitalization.
- 8 Pharmacogenetic sampling informed consent must be obtained prior to any blood being taken for PGx research. Sample should be drawn prior to dosing on Day 0. However, the sample may be collected at any time during the study.
- 9 Refer to Appendix 3. SLICC/ACR Damage Index is only performed at Screening and Week 52 (but not earlier if a subject discontinues study agent).
- 10 If a subject withdraws consent to participate in the first year monthly study visits, it is requested that the site attempt to obtain consent to contact the subject at Week 52 and annually for Years 2 through 5 (Week 260) to assess mortality and malignancy (including NMSC).
- 11 Following the study, all subjects will be contacted annually through Year 5 (Week 260) to assess mortality and malignancy (including NMSC).

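### The only inferential SLICC/ACR damage model is fitted in subjects who completed study agent, a group defined after randomisation; the same model should also be run on all subjects scored at Week 52

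*SAP*

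**What the plan says.** All SLICC analyses are in Section 12.2.3 of the Week 52 RAP (effective 18-OCT-2018).

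- **The model (12.2.3.2).** Worsening, meaning any increase in score from baseline to Week 52, is compared between arms by logistic regression. The table is to show "the odds ratio and 95% CI versus placebo, and a p-value for the odds ratio". The analysis set is restricted: only subjects who finish study agent through Week 48 and also "complete the study to Week 52 with a baseline and post-baseline assessment will be included in the analysis".
- **Covariates.** "The independent variables in the model will include treatment group and randomization strata per the eCRF" (steroid dose, region, SELENA SLEDAI), plus baseline SLICC score. All are measured before treatment.
- **The wider set (12.2.3.2).** "A summary will also be produced for subjects who complete the study through 52 weeks, i.e. subjects with off-treatment data will be included". That table gives the number and percentage with "worsening in their SLICC/ACR Damage Index score by treatment group and the treatment difference versus placebo". No model, odds ratio, CI or p-value is specified for it.
- **Other SLICC outputs.** "The change from baseline in SLICC/ACR Damage Index score at Week 52 will be summarized for belimumab and placebo", once in treatment completers and once in study completers. Organ-domain and subgroup summaries are in treatment completers only. All available SLICC data are listed.

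Section 12 makes ITT the default for efficacy unless otherwise stated, and 12.2.3.2 states otherwise. On data collection, Protocol Section 6.5 keeps subjects who stop study agent on study through Week 52, and footnote 9 of Table 6-1 says "SLICC/ACR Damage Index is only performed at Screening and Week 52 (but not earlier if a subject discontinues study agent"). RAP Section 9.5.19 adds that subjects who withdraw from the study itself have no Week 52 score.

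**The concern.** Randomisation makes the two arms comparable at Day 0. It does not make those who finish study agent in one arm comparable with those who finish in the other, because finishing can depend on how treatment went. The covariates are all pre-treatment and cannot account for why a subject stopped.

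The reasons for stopping can also be linked to the outcome. Under Protocol Sections 5.5.1 and 6.5, a subject who needs a prohibited medication, including another biologic, comes off study agent but stays on study. The damage index itself scores malignancy and osteomyelitis (RAP Appendix 5) and end-stage renal disease (RAP 9.5.19). A subject who stops study agent because of such an event can worsen on SLICC through that same event, and then does not enter the model.

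At stake is the reading of the one SLICC result that carries a p-value. It would naturally be taken as a randomised comparison of damage accrual, but it is a comparison of two selected groups.

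**Working it through.** **Step 1: which data exist and where they go.** The plan states no rate, power or sample size for SLICC, so there is no figure of its own to reproduce.

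| Subject | Week 52 SLICC collected? | In descriptive worsening table? | In the model? |
|---|---|---|---|
| Completes study agent and study | Yes | Yes | Yes |
| Stops study agent, completes study | Yes | Yes (study-completer table) | No |
| Withdraws from study or dies | No | No | No |

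The second row is the point: the outcome is collected and tabulated, but not modelled.

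**Step 2: illustrative size.** All inputs are assumptions:

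- stopping study agent but assessed at Week 52: placebo d_P = 10-20%, belimumab d_B = 8-15%
- worsening risk in completers: 6% in both arms, so the completer OR is 1.00
- worsening risk in stoppers: s = 12-18%, the same in both arms

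Risk among all assessed subjects in an arm = 0.06 + d × (s − 0.06). OR = [p_B/(1 − p_B)] / [p_P/(1 − p_P)].

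| s | d_P | d_B | p_B | p_P | OR, all assessed |
|---|---|---|---|---|---|
| 12% | 10% | 8% | 0.0648 | 0.0660 | 0.98 |
| 18% | 20% | 15% | 0.0780 | 0.0840 | 0.92 |
| 18% | 20% | 8% | 0.0696 | 0.0840 | 0.82 |
| 18% | 10% | 15% | 0.0780 | 0.0720 | 1.09 |

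The last two rows are the extremes over the stated ranges. The sign depends on which arm loses more subjects.

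**Step 3: equal stopping rates.** If 15% stop in each arm and stoppers have the same risk in both arms, the all-assessed OR stays at 1.00. If stopper risk is instead 12% on belimumab and 18% on placebo, p_B = 0.06 + 0.15 × 0.06 = 0.069 and p_P = 0.06 + 0.15 × 0.12 = 0.078, so the OR is 0.88. With the stopper risks swapped it is 1.14. Equal rates alone therefore do not guarantee comparability.

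**Step 4: the test when there is no true effect.** Assume 2,000 per arm, all reaching Week 52, the same overall worsening risk in both arms (6% or 10%), and stopper risk 1.5 to 3 times completer risk.

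| Stopping, belimumab / placebo | Completer-only OR | Rejection rate of the nominal 0.05 test |
|---|---|---|
| 20% / 20% | 1.00 | 0.05 |
| 20% / 25% | 1.02-1.08 | 0.053-0.082 |
| 20% / 30% | 1.05-1.15 | 0.060-0.164 |

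**Step 5: precision.** With 1:1 allocation, the Step 2 rates drop (10 + 8)/2 = 9% to (20 + 15)/2 = 17.5% of assessed subjects. Counting subjects, the CI on the log-odds scale widens by √(1/0.91) = 1.048 to √(1/0.825) = 1.101, about 5-10%. Under these assumptions stoppers have more events, so subject counts understate the loss. Taking the variance of log OR as the sum over arms of 1/[m p(1 − p)], where m is the number in the analysis, the ratio of standard errors runs from 1.09 (s = 12%, 10%/8%) to 1.26 (s = 18%, 20%/15%).

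**The case against.** Several points on the other side stand.

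- **Data are not discarded.** A reader might infer that the plan throws away the scores of subjects who stopped. It does not: they are in the study-completer change summary, the study-completer worsening table and the listing. An unadjusted odds ratio and CI could be computed from the worsening table. What is missing is the adjusted model on that set.
- **Imbalance is not expected.** RAP Section 11.1.1 does not anticipate a difference between arms in exposure or study duration. With equal stopping and equal stopper risk, Steps 3 and 4 show no bias. That limits the concern but does not remove it, since different kinds of subject may stop in each arm.
- **The wider set is also selected.** It still conditions on survival and on not withdrawing from the study. It also includes off-treatment subjects who may have started other biologics, including commercial belimumab (Protocol 5.5.1, RAP 10.4). It therefore answers a treatment-policy question, while the completer model aims at damage under full treatment. Both questions are legitimate, but only the wider set avoids selection on study-agent completion.
- **Low rank.** RAP Section 2.2.3 says SLICC is not an explicit protocol endpoint. It sits under other efficacy analyses, is not in the headline list (16.3), and has no multiplicity-controlled claim attached (8.4).
- **Timing.** The Years 2 to 5 RAP (Section 1) records unblinding on 2-JAN-2019 and states that the Week 52 analyses have been produced and reported.

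**Conclusion.** The point holds as a minor one. The only SLICC analysis with an odds ratio, CI and p-value conditions on completing study agent, departs from the ITT default without a stated reason, and omits Week 52 scores that the trial collects and tabulates.

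A reader might go further and infer that the result is biased in favour of one arm. The documents do not support that, because they give no stopping rate and no worsening rate. Under the assumed ranges a completer OR of 1.00 corresponds to about 0.82-1.09 in all assessed subjects, which spans both directions. A narrower interval wholly below 1, such as 0.92-0.98, appears only if low stopping rates are paired with low and high with high, which always gives placebo more stoppers. The loss of precision, about 5-10% on a subject-count basis, rests on the same assumed rates. Nothing here touches the primary safety analyses, which do not use this analysis set.

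**What to change.** Fit the same logistic model, with the same covariates, to all ITT subjects who have a baseline and a Week 52 SLICC assessment, regardless of study-agent completion. Report the odds ratio, 95% CI and p-value, give this result priority in interpretation, and keep the treatment-completer model as supportive. Because the Week 52 results are already reported, present a model added now as supplementary and post hoc, beside the prespecified one.

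State two limits with it: the set still conditions on surviving and not withdrawing from the study, and it includes subjects who may have taken other biologics after stopping study agent. Tabulating, by arm, how many subjects stopped study agent but were assessed at Week 52, with their worsening rate, would replace the assumptions above with observed figures.

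The cost is one change of population flag, one model run and one table. No new data are needed.
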